# 6.2 DATA SHARING PLANS

6.2.1 Human Data Sharing Plan

# What data will be shared?

I will share human data generated in this research for future research as follows:

\_X\_\_Coded, linked data in an NIH-funded or approved public repository.

\_X\_Coded, linked data in BTRIS (automatic for activities in the Clinical Center)

 $\underline{X}$  Coded, linked or identified data with approved outside collaborators under appropriate agreements.

# How and where will the data be shared?

Data will be shared through:

\_X\_\_An NIH-funded or approved public repository. Insert name or names:: ClinicalTrials.gov.

\_X\_BTRIS (automatic for activities in the Clinical Center)

\_X\_Approved outside collaborators under appropriate individual agreements.

\_X\_ Publication and/or public presentations.

# When will the data be shared?

\_X\_Before publication.

\_X\_ At the time of publication or shortly thereafter.

6.2.2 Genomic Data Sharing Plan

The present protocol, which ascertains transcriptomic data from 192 genes, does not apply to the GDS policy. The GDS policy states that RNA sequencing data from 100-sample threshold need to be shared. This protocol will not meet the 100 sample threshold.

## 6.3 **RESPONSE CRITERIA**

Restaging bone scans and/or CT scan of chest, abdomen and pelvis will be obtained at prior to Cycle 3 and every 3 cycles thereafter.

Progression will be evaluated in this study using the international criteria proposed by the Prostate Cancer Working Group 3 (PCWG3) guideline(2) and/or the revised Response Evaluation Criteria in Solid Tumors (RECIST) guideline (version 1.1).(62)

Changes in the largest diameter (unidimensional measurement) of the tumor lesions and the shortest diameter in the case of malignant lymph nodes are used in the RECIST criteria.

Changes in PSA and measurable lesions will be analyzed for efficacy according to PCWG3 recommendations. The recommended PSA progressions criteria will not be applied to the study as the criteria are arbitrarily proposed and do not necessarily reflect overall disease status. PSA values will be captured at each visit and PSA declines and progression will be followed. PSA is not sufficient in the evaluation of disease progression in this participant population. This is consistent with the recent recommendations by the Prostate Cancer Clinical Trials Working Group 2. Progression will be determined by radiographic evidence as discussed below or by clinical symptoms (symptomatic clinical progression).

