**Design:** 

- The study will be conducted using an optimal two stage Phase II design (8 participants, expandable to 21 participants total) aimed to determine the percentage of participants with a PSA decline of greater than 50% or stable disease at 5 months.
- The first 3 to 6 participants enrolled on study will follow a lead-in dosing scheme to confirm the safety of the combination (CRLX101 12 mg/m^2 every 2 weeks for the first two cycles, followed by CRLX101 15 mg/m^2 every 2 weeks at the start of cycle 3, with enzalutamide 160 mg administered once daily starting on cycle 1 day 2) prior to initiation of the optimal two stage study design.
- For participants enrolled on study following the lead-in, the confirmed tolerable dose of CRLX101 will be administered via IV infusion every 2 weeks. Enzalutamide 160 mg will be administered orally once daily beginning on cycle 1 day 2.
- Blood and urine will be collected at multiple time points for PK and PD analyses.
- Tumor assessments will be made using Tc bone scintography and/or CT scan (chest, abdomen, and pelvis) at baseline, prior to Cycle 3 and every 3 cycles thereafter.
- The accrual ceiling for the study is set at 30 participants.

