## Table **6:** Study Calendar

		Cycle 1		Cycle 2		Subsequent	Cycles	se vion	of ent	erm Up	
Procedure	 Screening/ Baseline	Day 1	Day 2	Day 15	Day 1	Day 15	Day 1	Day 15	 Disease Progression	 End of Treatment	 Long Term Follow-Up
History and PE	X	Х		X	X	Х	X	X	Х	Х	
Vital signs	X	Х		X	X	Х	X	X	X	Х	
ECOG Performance Score	X										
 Pathologic Confirmation of Dx	X										
 CBC/Diff	X	Х		Х	Х	Х	X	X	X		
 Acute Care Panel w/ Mineral Panel, Hepatic Panel, LDH, CK, Uric Acid, Total Protein	 X	Х		Х	X	Х	X	X	X		
 Urinalysis	 X	Х				Х					
Serum PSA	X	X		X	X	X	X	X	X		
Serum Testosterone	X	X			X		X		X		
 EKG	X	X		X	X						
Tumor Assessment: CT scan (chest, abdomen & pelvis), Tc bone scintography	X						 X		X		

		Cycle 1		Cycle 2		Subsequent Cycles		se tion	of ent	erm Up	
Procedure	 Screening/ Baseline	Day 1	Day 2	Day 15	Day 1	Day 15	Day 1	Day 15	 Disease Progression	 End of Treatment	 Long Term Follow-Up
CRLX101		Х		X	X	Х	Х	X			
Enzalutamide			X					•			
 Plasma PK		Х				Х					
 Urine PK		Х				Х					
 VEGF Biomarker, CTC, and Whole Blood Collection		X				X	 X		X		
 NanoString Sample Collection		Х				Х			X		
Adverse Events		X		X	X	Х	X	X	X	Х	
Concomitant Medications	X	X		X	X	X	X	X	X	Х	
 APTT, INR	X										
Survival Phone Call											Х

Baseline procedures are performed within 2 weeks of initiation of study therapy. Screening labs may also be used as baseline/Day 1 labs if performed within two weeks of study initiation. Height and weight must be done within 14 days of the first study dose.

To be completed on the day disease progression is noted according to PCWG3 and/or RECIST criteria. May be completed within 30 days or at end of treatment visit if logistically necessary and feasible. Subject may also be contacted by phone to assess adverse events if unwilling or unable to come to NIH."

To be completed within 30 days after the last dose of study therapy, presuming logistically feasible. The study team may contact the participant by phone to assess adverse events if unwilling or unable to come to NIH.

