# 6.3.1 Disease Parameters

Measurable disease: Measurable lesions are defined as those that can be accurately measured in at least one dimension (longest diameter to be recorded) as:

- By chest x-ray:  $\geq 20$  mm;
- By CT scan:
  - Scan slice thickness 5 mm or under: as  $\geq 10$  mm
  - Scan slice thickness >5 mm: double the slice thickness
- With calipers on clinical exam:  $\geq 10$  mm.

All tumor measurements must be recorded in millimeters (or decimal fractions of centimeters).

Malignant lymph nodes. To be considered pathologically enlarged and measurable, a lymph node must be  $\geq 15$  mm in short axis when assessed by CT scan (CT scan slice thickness recommended to be no greater than 5 mm). At baseline and in follow-up, only the short axis will be measured and followed.

Non-measurable disease. All other lesions (or sites of disease), including small lesions (longest diameter <10 mm or pathological lymph nodes with  $\geq$ 10 to <15 mm short axis), are considered non-measurable disease. Bone lesions, leptomeningeal disease, ascites, pleural/pericardial effusions, lymphangitis cutis/pulmonitis, inflammatory breast disease, and abdominal masses (not followed by CT or MRI), are considered as non-measurable.

Note: Cystic lesions that meet the criteria for radiographically defined simple cysts should not be considered as malignant lesions (neither measurable nor non-measurable) since they are, by definition, simple cysts.

'Cystic lesions' thought to represent cystic metastases can be considered as measurable lesions, if they meet the definition of measurability described above. However, if non-cystic lesions are present in the same participant, these are preferred for selection as target lesions.

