### 6.3.3.5 Evaluation of Best Overall Response

The best overall response is the best response recorded from the start of the treatment until disease progression/recurrence (taking as reference for progressive disease the smallest measurements recorded since the treatment started). The participant's best response assignment will depend on the achievement of both measurement and confirmation criteria.

Target Lesions	Non-Target Lesions	New Lesions	Overall Response	Best Overall Response when Confirmation is Required*
CR	CR	No	CR	≥4 wks. Confirmation**
CR	Non-CR/Non- PD	No	PR	
CR	Not evaluated	No	PR	>4 wks. Confirmation**
PR	Non-CR/Non- PD/not evaluated	No	PR	
SD	Non-CR/Non- PD/not evaluated	No	SD	Documented at least once > 4 wks. from baseline**
PD	Any	Yes or No	PD	no prior SD, PR or CR

For Participants with Measurable Disease (i.e., Target Disease)

Ar	ıy	PD***	Yes or No	PD			
Ar	ıy	Any	Yes	PD			
* **	See RECIST 1.1 manuscript for further details on what is evidence of a new lesion.						
***	In exceptional circumstances, unequivocal progression in non-target lesions may be accepted as disease progression.						
Note :	Participants with a global deterioration of health status requiring discontinuation of treatment without objective evidence of disease progression at that time should be reported as " symptomatic deterioration ." Every effort should be made to document the objective progression even after discontinuation of treatment.						

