# For Participants with Non-Measurable Disease (i.e., Non-Target Disease)

Non-Target Lesions	New Lesions	Overall Response
CR	No	CR
Non-CR/non-PD	No	Non-CR/non-PD*
Not all evaluated	No	not evaluated
Unequivocal PD	Yes or No	PD
Any	Yes	PD

\* 'Non-CR/non-PD' is preferred over 'stable disease' for non-target disease since SD is increasingly used as an endpoint for assessment of efficacy in some trials so to assign this category when no lesions can be measured is not advised

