#### 12.5.2 Risks from Radiation Exposure

The procedures for performing the CT scans (chest/abdomen/pelvis) and Tc-99 whole body scintography scans will follow clinical policies, no special procedures apply to these additional assessments for research purposes. In summary, subjects may receive additional radiation exposure in one year from up to four (4) CT scans of the chest, abdomen, and pelvis, and four (4) Tc-99 whole body scintography scans. Radiation exposure is associated with an increased risk of cancer.

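### Restaging may use one scan type or both, and under the stated rules a stable CT without a bone scan at C6D1 can be scored as a primary success

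*Combined protocol and SAP*

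**What the plan says.** **Which scans are done.** Section 6.3 states: "Restaging bone scans and/or CT scan of chest, abdomen and pelvis will be obtained at prior to Cycle 3 and every 3 cycles thereafter". The Design part of the précis has "bone scintography and/or CT scan (chest, abdomen, and pelvis) at baseline, prior to Cycle 3 and every 3 cycles thereafter". Table 6 (section 3.4) has a single row that begins "Tumor Assessment: CT scan (chest, abdomen" and goes on to name the bone scan after a comma, with no alternative offered. Section 12.5.2 allows, for one year, up to "four (4) CT scans of the chest, abdomen, and pelvis, and four (4) Tc-99 whole body scintography scans". Screening (2.2) obtains both scans and lets MRI replace CT.

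**How a missing scan is scored.** Section 6.3.1 places "Bone lesions, leptomeningeal disease, ascites, pleural/pericardial effusions" among non-measurable disease, so bone metastases are followed as non-target lesions. Section 6.3.3.5 has two response tables:

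- Measurable disease: target lesions stable, non-target status "Non-CR/Non- PD/not evaluated" and no new lesions gives overall SD. The confirmation column asks only that this be "Documented at least once", four weeks or more from baseline.
- Non-measurable disease: the row "Not all evaluated" gives an overall response of not evaluated.

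**What counts as success.** Sections 1.1.1 and 10.1.1 accept a PSA decline of at least 50% or stability on imaging, without naming a modality. Section 10.2 defines the imaging limb as stability on bone scan. Footnote 12 of Table 6 puts the primary assessment at C6D1. For efficacy evaluability, section 10.2 asks for one dose of CRLX101 and one follow-up imaging study of unspecified type.

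**The concern.** Stable disease is itself a success in this trial, so the rule that produces SD from incomplete imaging feeds the primary endpoint directly. Section 6.3.3.3 defines bone progression by at least two new lesions on bone scan. If that scan is not done, bone progression cannot be declared by that rule. A participant with measurable nodes and bone metastases could then be counted a success on the nodes alone. The trial is single-arm, so there is no control group in which the same error would cancel. An error of this kind raises the success fraction that is compared with the fixed 25% benchmark.

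**Working it through.** **Step 1. Is the wording inconsistent?** The précis and 6.3 permit one modality; Table 6 lists both. The count in 12.5.2 fits both being done each time. With 28-day cycles, cycle c starts on day 28(c − 1) + 1, so C3, C6, C9 and C12 start on days 57, 141, 225 and 309, and C15 on day 393. That is four on-treatment restagings within a year, matching four CTs and four bone scans.

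**Step 2. Does the text lead from a skipped bone scan to a success?**

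1. A participant has measurable soft-tissue disease and bone metastases at baseline. The bone lesions are non-target (6.3.1).
2. At C6D1 only CT is done, as 6.3 permits. Target lesions are SD; bone is not evaluated.
3. The measurable-disease row gives overall SD, provided the new-lesions column is entered as No. The plan does not say whether No may be entered without a bone scan.
4. He is evaluable under 10.2 because he has a follow-up imaging study.
5. He is stable on imaging under 1.1.1 and 10.1.1, hence a success.

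If 10.2's bone-scan wording governs, step 5 fails. The reverse case then opens: a stable bone scan with no CT satisfies the imaging limb while soft-tissue disease is unassessed.

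**Step 3. Reproduce the design (10.2).** Inputs: p0 = 0.25, p1 = 0.50, alpha 0.10, beta 0.20; stop at 2 or fewer successes of 8; positive at 8 or more of 21. With b(n, x, p) the binomial probability:

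- P(early termination at 0.25) = 0.10011 + 0.26697 + 0.31146 = 0.67854. The plan states 67.9%, which reproduces.
- P(positive) = sum over x = 3 to 8 of b(8, x, p) × P(Bin(13, p) ≥ 8 − x). This is 0.098 at p = 0.25 and 0.811 at p = 0.50, within the stated error limits.

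**Step 4. Sensitivity to misclassification.** Let f be the share of true non-successes scored SD because a compartment was not imaged. The apparent rate at a true 25% is 0.25 + 0.75f. The documents give no value for f; every value below is an assumption.

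| f | Apparent rate | P(early termination) | P(positive) |
|---|---|---|---|
| 0 | 0.25 | 0.679 | 0.098 |
| 2% | 0.265 | 0.641 | 0.128 |
| 5% | 0.2875 | 0.584 | 0.181 |
| 10% | 0.325 | 0.489 | 0.289 |

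One way to bracket f for the CT-only route is as a product of three assumed shares: measurable disease 30% to 70%, progression in bone only among non-successes 20% to 40%, bone scan skipped 10% to 50%. The low end is 0.3 × 0.2 × 0.1 = 0.6%, giving P(positive) = 0.106. The high end is 0.7 × 0.4 × 0.5 = 14%, giving 0.388.

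**The case against.** The strongest reply is that the plan, read as a whole, already expects both scans. Section 6.3.1 wants the status of each non-target lesion noted throughout follow-up, and 6.3.2 says each lesion should be assessed by the same method at baseline and follow-up. With Table 6 and 12.5.2, the and/or wording can be read as matching scans to the participant's disease. That reading is reasonable and probably intended. But the text in 6.3.2 is a recommendation, Table 6 lists both scans without stating that both are required, and none of these places says how a missing scan is scored.

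A second reply is that 10.2 asks for stability on bone scan, so the CT-only success does not arise. That is correct if 10.2 governs. Nothing says that it does, and it leaves the reverse gap. A third is that new lesions cannot properly be recorded as absent without a bone scan. The plan could say so, but does not.

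A reader might infer that every skipped scan pushes a participant towards success. The documents do not support that. A participant without measurable disease whose lesions are incompletely evaluated is scored not evaluated, and the measurable-disease table has no SD row for unassessed target lesions. Clinical progression (6.3.3.4) can also be declared without any scan.

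**Conclusion.** The concern holds in a limited form. The restaging requirement is worded inconsistently. Under the stated rules, a participant with disease in both bone and soft tissue, stable in the compartment that was imaged, can be counted a success with the other compartment unassessed. Which compartment is left open depends on whether the wording of 1.1.1 and 10.1.1 or that of 10.2 governs. The CT-only route also depends on the absence of new lesions being recorded without a bone scan.

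Within that group the error runs towards success. Its size cannot be derived from the documents: assumed misclassification of 2% to 10% of true non-successes raises the false-positive probability from 0.098 to between 0.128 and 0.289. It would be wrong to infer that the trial's actual error rate is any of these figures. If both scans are done at every restaging, as Table 6 suggests, this bias does not arise. The sample size and boundaries are not in question.

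**What to change.** 1. In the précis and 6.3, replace the and/or wording with a requirement for both bone scan and CT, matching Table 6, with MRI allowed in place of CT as in 2.2.
2. Use one definition of the imaging limb in the précis, 1.1.1, 10.1.1 and 10.2.
3. State in 6.3.3.5 and 10.2 that the imaging limb is met at C6D1 only if all disease sites present at baseline were imaged (bone by bone scan, soft tissue by CT or MRI) and the absence of new lesions was judged on both scans. Otherwise the imaging limb is not met, and the participant is scored on the PSA limb and stays in the denominator.

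The cost is wording. No scan is added beyond those listed in Table 6, and the 2/8 and 7/21 boundaries stay as they are. The downside is that a missed scan counts against success, which costs some power if scans are often missed. Treating it this way, rather than as not evaluated, is a deliberate conservative choice and should be stated as one.

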# 6.3.1 Disease Parameters

Measurable disease: Measurable lesions are defined as those that can be accurately measured in at least one dimension (longest diameter to be recorded) as:

- By chest x-ray:  $\geq 20$  mm;
- By CT scan:
  - Scan slice thickness 5 mm or under: as  $\geq 10$  mm
  - Scan slice thickness >5 mm: double the slice thickness
- With calipers on clinical exam:  $\geq 10$  mm.

All tumor measurements must be recorded in millimeters (or decimal fractions of centimeters).

Malignant lymph nodes. To be considered pathologically enlarged and measurable, a lymph node must be  $\geq 15$  mm in short axis when assessed by CT scan (CT scan slice thickness recommended to be no greater than 5 mm). At baseline and in follow-up, only the short axis will be measured and followed.

Non-measurable disease. All other lesions (or sites of disease), including small lesions (longest diameter <10 mm or pathological lymph nodes with  $\geq$ 10 to <15 mm short axis), are considered non-measurable disease. Bone lesions, leptomeningeal disease, ascites, pleural/pericardial effusions, lymphangitis cutis/pulmonitis, inflammatory breast disease, and abdominal masses (not followed by CT or MRI), are considered as non-measurable.

Note: Cystic lesions that meet the criteria for radiographically defined simple cysts should not be considered as malignant lesions (neither measurable nor non-measurable) since they are, by definition, simple cysts.

'Cystic lesions' thought to represent cystic metastases can be considered as measurable lesions, if they meet the definition of measurability described above. However, if non-cystic lesions are present in the same participant, these are preferred for selection as target lesions.

Target lesions. All measurable lesions up to a maximum of 2 lesions per organ and 5 lesions in total, representative of all involved organs, should be identified as **target lesions** and recorded and measured at baseline. Target lesions should be selected on the basis of their size (lesions with the longest diameter), be representative of all involved organs, but in addition should be those that lend themselves to reproducible repeated measurements. It may be the case that, on occasion, the largest lesion does not lend itself to reproducible measurement in which circumstance the next largest lesion which can be measured reproducibly should be selected. A sum of the diameters (longest for non-nodal lesions, short axis for nodal lesions) for all target lesions will be calculated and reported as the baseline sum diameters. If lymph nodes are to be included in the sum, then only the short axis is added into the sum. The baseline sum diameters will be used as reference to further characterize any objective tumor regression in the measurable dimension of the disease.

Non-target lesions. All other lesions (or sites of disease) including any measurable lesions over and above the 5 target lesions should be identified as **non-target lesions** and should also be recorded at baseline. Measurements of these lesions are not required, but the presence, absence, or in rare cases unequivocal progression of each should be noted throughout follow-up.

#### 6.3.2 Methods for Evaluation of Measurable Disease

All measurements should be taken and recorded in metric notation using a ruler or calipers. All baseline evaluations should be performed as closely as possible to the beginning of treatment and never more than 4 weeks before the beginning of the treatment.

The same method of assessment and the same technique should be used to characterize each identified and reported lesion at baseline and during follow-up. Imaging-based evaluation is preferred to evaluation by clinical examination unless the lesion(s) being followed cannot be imaged but are assessable by clinical exam.

Clinical lesions: Clinical lesions will only be considered measurable when they are superficial (e.g., skin nodules and palpable lymph nodes) and  $\geq 10$  mm diameter as assessed using calipers (e.g., skin nodules). In the case of skin lesions, documentation by color photography, including a ruler to estimate the size of the lesion, is recommended.

Chest x-ray: Lesions on chest x-ray are acceptable as measurable lesions when they are clearly defined and surrounded by aerated lung. However, CT is preferable.

Conventional CT and MRI: This guideline has defined measurability of lesions on CT scan based on the assumption that CT slice thickness is 5 mm or less. If CT scans have slice thickness greater than 5 mm, the minimum size for a measurable lesion should be twice the slice thickness. MRI is also acceptable in certain situations (e.g. for body scans).

Use of MRI remains a complex issue. MRI has excellent contrast, spatial, and temporal resolution; however, there are many image acquisition variables involved in MRI, which greatly impact image quality, lesion conspicuity, and measurement. Furthermore, the availability of MRI is variable globally. As with CT, if an MRI is performed, the technical specifications of the

scanning sequences used should be optimized for the evaluation of the type and site of disease. Furthermore, as with CT, the modality used at follow-up should be the same as was used at baseline and the lesions should be measured/assessed on the same pulse sequence. It is beyond the scope of the RECIST guidelines to prescribe specific MRI pulse sequence parameters for all scanners, body parts, and diseases. Ideally, the same type of scanner should be used and the image acquisition protocol should be followed as closely as possible to prior scans. Body scans should be performed with breath-hold scanning techniques, if possible.

PET-CT: At present, the low dose or attenuation correction CT portion of a combined PET-CT is not always of optimal diagnostic CT quality for use with RECIST measurements. However, if the site can document that the CT performed as part of a PET-CT is of identical diagnostic quality to a diagnostic CT (with IV and oral contrast), then the CT portion of the PET-CT can be used for RECIST measurements and can be used interchangeably with conventional CT in accurately measuring cancer lesions over time. Note, however, that the PET portion of the CT introduces additional data which may bias an investigator if it is not routinely or serially performed.

Ultrasound: Ultrasound is not useful in assessment of lesion size and should not be used as a method of measurement. Ultrasound examinations cannot be reproduced in their entirety for independent review at a later date and, because they are operator dependent, it cannot be guaranteed that the same technique and measurements will be taken from one assessment to the next. If new lesions are identified by ultrasound in the course of the study, confirmation by CT or MRI is advised. If there is concern about radiation exposure at CT, MRI may be used instead of CT in selected instances.

Endoscopy, Laparoscopy: The utilization of these techniques for objective tumor evaluation is not advised. However, such techniques may be useful to confirm complete pathological response when biopsies are obtained or to determine relapse in trials where recurrence following complete response (CR) or surgical resection is an endpoint.

Cytology, Histology: These techniques can be used to differentiate between partial responses (PR) and complete responses (CR) in rare cases (e.g., residual lesions in tumor types, such as germ cell tumors, where known residual benign tumors can remain).

The cytological confirmation of the neoplastic origin of any effusion that appears or worsens during treatment when the measurable tumor has met criteria for response or stable disease is mandatory to differentiate between response or stable disease (an effusion may be a side effect of the treatment) and progressive disease.

FDG-PET: While FDG-PET response assessments need additional study, it is sometimes reasonable to incorporate the use of FDG-PET scanning to complement CT scanning in assessment of progression (particularly possible 'new' disease). New lesions on the basis of FDG-PET imaging can be identified according to the following algorithm:

- a. Negative FDG-PET at baseline, with a positive FDG-PET at follow-up is a sign of PD based on a new lesion.
- b. No FDG-PET at baseline and a positive FDG-PET at follow-up: If the positive FDG-PET at follow-up corresponds to a new site of disease confirmed by CT, this is PD. If the positive FDG-PET at follow-up is not confirmed as a new site of disease on CT,

additional follow-up CT scans are needed to determine if there is truly progression occurring at that site (if so, the date of PD will be the date of the initial abnormal FDG-PET scan). If the positive FDG-PET at follow-up corresponds to a pre-existing site of disease on CT that is not progressing on the basis of the anatomic images, this is not PD.

c. FDG-PET may be used to upgrade a response to a CR in a manner similar to a biopsy in cases where a residual radiographic abnormality is thought to represent fibrosis or scarring. The use of FDG-PET in this circumstance should be prospectively described in the protocol and supported by disease-specific medical literature for the indication. However, it must be acknowledged that both approaches may lead to false positive CR due to limitations of FDG-PET and biopsy resolution/sensitivity.

Note: A 'positive' FDG-PET scan lesion means one which is FDG avid with an uptake greater than twice that of the surrounding tissue on the attenuation corrected image.

- 6.3.3 Response Criteria
- 6.3.3.1 Evaluation of Target Lesions

Complete Response (CR): Disappearance of all target lesions. Any pathological lymph nodes (whether target or non-target) must have reduction in short axis to <10 mm.

Partial Response (PR): At least a 30% decrease in the sum of the diameters of target lesions, taking as reference the baseline sum of diameters.

Progressive Disease (PD): At least a 20% increase in the sum of the diameters of target lesions, taking as reference the smallest sum on study (this includes the baseline sum if that is the smallest on study). In addition to the relative increase of 20%, the sum must also demonstrate an absolute increase of at least 5 mm. (Note: the appearance of one or more new lesions is also considered progressions).

Stable Disease (SD): Neither sufficient shrinkage to qualify for PR nor sufficient increase to qualify for PD, taking as reference the smallest sum of diameters while on study.

